### 2.5.1.2 Multiple assessments within visit windows

When there are multiple assessments in a particular visit window, the following rules are applied to select one value “representing” the subject in summary statistics in a visit window (see [Table 2-2](#)).

For baseline assessment definition see [Section 2.1.2](#). For post-baseline visit windows the following applies (unless otherwise specified):

- for *quantitative variables*, the *closest* to the scheduled day is chosen (if two assessments have the same distance, then the earlier one will be chosen);
- for *qualitative variables*, the *worst* record is selected. It is noted that in the analyses performed, *worst* case is always well defined (e.g., for urine protein values “+” and “++”, the worst case is defined as “++”),
- in case qualitative variables are based on quantitative variables, e.g. DLQI response, the visit will be assigned to the quantitative variable, and this visit will be used for the derived qualitative variable.

**Table 2-2 Rules for selecting values for analysis within a given visit window**

Timing of measurement	Type of data	Rule
Baseline	All data	See Section 2.1.2
Post-baseline efficacy	All data except for PRO e.g., HiSCR, HS-PGA	The measurement closest to the scheduled day will be used. In the event two measurements are taken equally apart (e.g., 1 day before target date and 1 day after), the earlier one will be used.
Post-baseline efficacy	PRO data	The measurement closest to the scheduled day will be used. In the event two measurements are taken equally apart (e.g., 1 day before target date and 1 day after), the earlier one will be used. For e-diary data, a cut-off at 3:00 PM is used to define the start of a new day. Anything entered before that time (no later than 2:59 PM) refers to the day before. If more than one measurement is taken on the same day (before the cut-off), the latest one will be used.
Post-baseline safety	Summary visit information (e.g. laboratory values, vital signs, etc.)	The (non-missing) measurement closest to the scheduled day will be used. In the event two measurements are taken equally apart (e.g., 1 day before target date and 1 day after), the earlier one will be used.
Post-baseline safety	Notable abnormalities (e.g. vitals signs) and CTCAE grades for laboratory values	The most extreme measurement in the window will be used. Note this means a subject can have a notably high and notably low measurement within an analysis period.

### 2.5.2 Prior and concomitant therapies

Medications will be identified using Novartis Drug and Therapy Dictionary (NovDTD) including Anatomical Therapeutic Chemical (ATC) code. Prior and concomitant treatments will be summarized by treatment group for the safety set unless otherwise specified. Concomitant treatments will be displayed for the Treatment Period. Also, prior and concomitant treatments will be listed.

Prior medications are defined as drugs taken and stopped prior to the first dose of study treatment. Any medication given at least once between the day of first dose of study treatment, and within 84 days after last dose will be a concomitant medication, including those which were started before first dose of study treatment and continued into the Treatment Period.

Prior or concomitant medication will be identified based on recorded or imputed start and end dates of medication taken. Medications collected in ‘Prior HS Medications’ CRF page are considered as prior medications. Therapies collected on ‘Prior HS non-drug therapy’ CRF page are considered as prior therapies. Further rules will be given in [Section 5.1.3](#).

Prior and concomitant medications will be summarized by treatment group in separate tables. Medications will be presented in alphabetical order, by category and preferred term. Tables will

also show the overall number and percentage of subjects receiving at least one drug of a particular category and at least one drug in a particular preferred term.

In addition, medical procedures and significant non-drug therapies as coded in MedDRA will be summarized.

Pain medication for HS (ibuprofen, tramadol and paracetamol) will be summarized by treatment group in separate tables. Medications will be presented in alphabetical order, by category and preferred term. Tables will also show the overall number and percentage of subjects receiving at least one drug of a particular category and at least one drug in a particular preferred term.

## 2.6 Safety analyses

All safety analyses will be based on the safety set.

Analysis of adverse events will be based on treatment emergent events, which are defined as events started on or after the first dose of study treatment or events present prior to the first dose of study treatment but increased in severity based on preferred term and on or before last dose + 84 days.

Other safety variables will be evaluated based on on-treatment events, which are defined as any events that happened after first dose of study treatment and on or before last dose + 84 days.

Safety analysis will be performed on actual treatment and the entire study period.

### 2.6.1 Adverse events (AEs)

For adverse events and other binary safety variables crude and exposure time adjusted incidence rates will be derived as described below and summarized in [Table 2-3](#).

All adverse events, serious adverse events will be listed with “treatment emergent” flag displayed.

**Table 2-3 Overview of analyses on some safety endpoints**

Analysis period	AEs & Risk management plans (RMP)	SAEs	AEs by severity	study treatment related AEs, death & other significant AEs	notables (lab/vitals)
Entire study period	• crude incidence • exp.time adjusted incidence	• crude incidence • exp.time adjusted incidence	• crude incidence	• crude incidence	• crude incidence

The crude incidence of treatment emergent adverse events will be summarized by primary System Organ Class (SOC) and Preferred Term (PT). Confidence intervals for the crude rate will be derived using the score method including continuity correction ([Newcombe 1998](#)) as described in [Section 5.4.2.1](#).

Adverse events will be summarized by presenting, for each treatment group, the number and percentage of subjects having at least one AE, having an AE in each primary system organ class and having each individual AE (preferred term). Summaries will also be presented for AEs by severity. If a particular AE “severity” is missing, this variable will be listed as missing and

treated as missing in summaries. If a subject reported more than one adverse event with the same preferred term, the adverse event with the greatest severity will be presented. If a subject reported more than one adverse event within the same primary system organ class, the subject will be counted only once with the greatest severity at the system organ class level, where applicable. AEs by severity will be provided by SOC and AEs by severity and PTs may be provided if required at ad-hoc basis.

The most common adverse events reported ( $\geq z\%$  in any treatment group by SOC and PT) will be presented in descending frequency according to its incidence in Any AIN457 group starting from the most common event. The threshold value  $z$  is set to 2 % but it may be updated following review of the dry run outputs.

Separate summaries will be provided for deaths, serious adverse events, other significant adverse events leading to discontinuation.

For the legal requirements of ClinicalTrials.gov and EudraCT, two required tables on treatment adverse events which are not serious adverse events with an incidence greater than 2% and on treatment serious adverse events and SAE suspected to be related to study treatment will be provided by system organ class and preferred term on the safety set population.

If for a same subject, several consecutive AEs (irrespective of study treatment causality, seriousness and severity) occurred with the same SOC and PT:

- a single occurrence will be counted if there is  $\leq 1$  day gap between the end date of the preceding AE and the start date of the consecutive AE
- more than one occurrence will be counted if there is  $> 1$  day gap between the end date of the preceding AE and the start date of the consecutive AE

For occurrence, the presence of at least one SAE / SAE suspected to be related to study treatment / non SAE has to be checked in a block e.g., among AEs in a  $\leq 1$  day gap block, if at least one SAE is occurring, then one occurrence is calculated for that SAE.

The number of deaths resulting from SAEs suspected to be related to study treatment and SAEs irrespective of study treatment relationship will be provided by SOC and PT.

Algorithms for AE date imputations will be provided in [Section 5.1.2](#).

## **2.6.2 Deaths**

Separate summary and listing will be provided for deaths.

## **2.6.3 Laboratory data**

The summary of laboratory evaluations will be presented for two groups of laboratory tests (hematology and serum chemistry).

Descriptive summary statistics for the change from baseline for the entire study period will be presented by laboratory test and treatment group. Change from baseline will only be summarized for subjects with both baseline and post baseline values and will be calculated as:

change from baseline = post baseline value – baseline value

All laboratory data will be listed with “on-treatment” flag displayed. In addition, Box and Whisker plots of hematology and serum chemistry will be provided for absolute values over time for Treatment period 1 and Entire study period.

For each parameter, the maximum change (maximum decrease and maximum increase) from baseline within Treatment Period will be summarized analogously.

In addition, shift tables will be provided for all parameters to compare a subject’s baseline laboratory evaluation relative to the most extreme laboratory test value within a Treatment Period. For the shift tables, the normal laboratory ranges will be used to evaluate whether a particular laboratory test value is normal, low, or high (including category “high and low”). These summaries will be presented by laboratory test and treatment group. Subjects with abnormal laboratory values will be listed and values outside the normal ranges will be flagged.

The following laboratory parameters will be analyzed with respect to numerical Common Terminology Criteria for Adverse Events (CTCAE) grades, given in [Table 2-4](#): hemoglobin, platelets, white blood cell count, neutrophils, lymphocytes, creatinine, total bilirubin (TBL), gamma-glutamyl transferase (GGT), alanine aminotransferase (ALT), aspartate aminotransferase (AST), alkaline phosphatase (ALP). CTCAE version 4.03 is implemented to be consistent with previous analyses.

The number and percentage of subjects with CTCAE grade newly occurring or worsening after baseline will be presented. These summaries will be split into hematology and chemistry.

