6.7.2 Instruction for prescribing and taking study treatment

Secukinumab solution for s.c. injection or placebo secukinumab solution (active or placebo, respectively) will be provided in pre-filled syringes (PFS).

Each subject will require one box with PFS per dose throughout the study:

- One secukinumab 300 mg, 2ml PFS **OR**

- One secukinumab placebo 300 mg, 2ml PFS.

All study treatment kits assigned to the subject by IRT during the study will be captured in the IRT system.

The first study treatment administration will occur at the baseline/randomization visit after the inclusion/exclusion criteria have been confirmed and all study scheduled assessments have been performed. All study assessments, including completion of Patient Reported Outcomes (PROs) and blood withdrawal, should be completed prior to the self-injection of study treatment.

All doses of study treatment (secukinumab and/or placebo) will be self-administered by the subject/ trained caregiver either at the study site after the study assessments for the visits have been completed or at home.

The first use at baseline and the Week 1 assessments of the self-injection will take place in the context of an observed assessment under the supervision of one site staff member. At the baseline visit, subjects will be instructed by the site staff on how to self-inject via the pre-filled syringe (Instructions for Use (IFU) containing detailed information about self-administration of study treatment should be provided to each subject at the beginning of the study). After providing detailed explanations/instructions, subjects will then be asked to raise any questions. Thereafter, they will proceed with self-injection. At Week 1, subjects will be asked to refer to the IFU and to proceed with self-injection of the actual study drug (i.e. without a detailed explanation/instruction on handling the syringe).

Home administrations (H) should be done at pre-defined visits (see [Section 3](#)). Home administration can be performed by the subject or trained caregiver. If the subject or caregiver is not able/confident to perform home administration, the subject will be allowed to return to the site for administration of the medication. However, during those visits no additional assessments will be required.

During home administrations, subjects will be instructed to contact the investigator/site staff in case they are experiencing any AE/SAEs or have any concerns.

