### **Baseline definitions**

For efficacy analyses,

- For HS Symptom Diary assessment and Patient’s Global assessment of Skin Pain, the average of the latest 7 assessments before the date of the first drug administration of the study treatment (or randomization date if there has been no drug administration) will be used as baseline. In case less than 4 diary entries prior to the first dose of the study treatment were available, baseline will be set to missing.
- For all other efficacy assessments, baseline is the last assessment (including unscheduled visits) obtained (on or) before the day of the first drug administration of the study treatment (or randomization date if there has been no drug administration).

All assessments obtained after first dose (day) of study treatment are considered as post-baseline unless otherwise specified.

For safety analyses, baseline is the last assessment (including unscheduled visits) obtained (on or) before the first dose (day) of study treatment. All assessments obtained after the first dose (day) of study treatment are considered as post-baseline unless otherwise specified.

Of note, baseline will be derived based on first dose day, exact dosing time is not considered.

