## **2.3 Analysis period and treatment groups**

### **2.3.1 Final Week 52 analysis**

The efficacy and safety analyses will be conducted up to Week 52 or Week 60, when all subjects have completed the study.

The efficacy will be conducted using the following treatment groups:

- AIN457 300mg Q2W (subjects randomized to secukinumab 300 mg every 2 weeks arm)
- AIN457 300mg Q4W (subjects randomized to secukinumab 300 mg every 4 weeks arm)
- PBO-AIN457 300mg Q2W (subjects randomized to placebo who switched to secukinumab 300 mg every 2 weeks arm at Week 16. Data is included after first intake of placebo.)
- PBO-AIN457 300mg Q4W (subjects randomized to placebo who switched to secukinumab 300 mg every 4 weeks arm at Week 16. Data is included after first intake of placebo.)

The safety will be conducted using the following treatment groups:

- AIN457 300mg Q2W (subjects randomized to secukinumab 300 mg every 2 weeks arm)
- AIN457 300mg Q4W (subjects randomized to secukinumab 300 mg every 4 weeks arm)
- Any AIN457 300mg Q2W (subjects randomized to secukinumab 300mg Q2W plus subjects randomized to placebo to secukinumab 300 mg every 2 weeks arm after their first intake of secukinumab)
- Any AIN457 300mg Q4W (subjects randomized to secukinumab 300mg Q4W plus subjects randomized to placebo to secukinumab 300 mg every 4 weeks arm after their first intake of secukinumab)
- Any AIN457 (this group combines the two groups “Any AIN457 300mg Q2W” and “Any AIN457 300mg Q4W”)

The subjects randomized to placebo to secukinumab 300 mg every 2 weeks arm and placebo to secukinumab 300 mg every 4 weeks arm will be counted in placebo until the day before the first secukinumab dose. Subsequently, they will be counted in Any AIN457 300mg Q2W or Any AIN457 300mg Q4W, respectively. AEs that occur starting on the day of taking the first secukinumab dose will be counted in Any AIN457 300mg Q2W or Any AIN457 300mg Q4W; other assessments, (i.e. efficacy, lab assessments) collected on the day of taking the first secukinumab dose will be counted in the placebo group.

Safety tables related to exposure adjustment incident rate will also display the placebo treatment group.

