**Table 2-4 CTCAE grades for laboratory parameters to be analyzed**

CTCAE v4.03 Term	Grade 1	Grade 2	Grade 3	Grade 4
HGB decreased (Anemia)	<LLN – 100 g/L	<100 – 80 g/L	<80 g/L	Life-threatening consequences; urgent intervention
Platelet count Decreased	<LLN – 75.0 x10e9 /L	<75.0 – 50.0 x10e9 /L	<50.0 – 25.0 x10e9 /L	<25.0 x 10e9 /L
White blood cell decreased	<LLN - 3.0 x 10e9 /L	<3.0 - 2.0 x 10e9 /L	<2.0 - 1.0 x 10e9 /L	<1.0 x 10e9 /L
Neutrophil count decreased	<LLN - 1.5 x 10e9 /L	<1.5 - 1.0 x 10e9 /L	<1.0 - 0.5 x 10e9 /L	<0.5 x 10e9 /L
Lymphocyte count decreased	<LLN - 0.8 x 10e9/L	<0.8 - 0.5 x 10e9 /L	<0.5 - 0.2 x 10e9 /L	<0.2 x 10e9 /L
Creatinine increased	>ULN - 1.5 x ULN	>1.5 - 3.0 x ULN	>3.0 - 6.0 x ULN	>6.0 x ULN
TBL increased	>ULN - 1.5 x ULN	>1.5 - 3.0 x ULN	>3.0 - 10.0 x ULN	>10.0 x ULN
GGT increased	>ULN - 2.5 x ULN	>2.5 - 5.0 x ULN	>5.0 - 20.0 x ULN	>20.0 x ULN
ALT increased	>ULN - 3.0 x ULN	>3.0 - 5.0 x ULN	>5.0 - 20.0 x ULN	>20.0 x ULN
AST increased	>ULN - 3.0 x ULN	>3.0 - 5.0 x ULN	>5.0 - 20.0 x ULN	>20.0 x ULN
ALP increased	>ULN - 2.5 x ULN	>2.5 - 5.0 x ULN	>5.0 - 20.0 x ULN	>20.0 x ULN

Shift tables will be presented comparing baseline laboratory result (CTCAE grade) with the worst results (expressed in CTCAE grade) during the treatment period analyzed.

The number and percentage of subjects with newly occurring liver enzyme abnormalities will also be summarized based on the event criteria given in [Table 2-5](#).

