## 2.6.4 Other safety data

### 2.6.4.1 Vital signs

Analysis in vital sign measurement using descriptive summary statistics for the change from baseline for visits up to Week 52 will be performed by vital sign parameters and treatment group. Change from baseline will only be summarized for subjects with both baseline and post-baseline values and will be calculated as:

$$\text{change from baseline} = \text{post-baseline value} - \text{baseline value}$$

All vital signs will be listed with “on-treatment” flag displayed. In addition, Box and Whisker plots of hematology and serum chemistry will be provided for absolute values over time for Treatment period 1 and Entire study period.

The number and percentage of subjects with newly occurring notable vital signs will be presented. Criteria for notable vital sign abnormalities are provided in [Table 2-6](#) below.

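### For placebo switchers the safety baseline precedes placebo, so an abnormality that arose on placebo and persists past the switch counts as new under 'Any AIN457'

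*SAP*

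**What the plan says.** **Baseline.** SAP 2.1.2: "For safety analyses, baseline is the last assessment (including unscheduled visits) obtained (on or) before the first dose (day) of study treatment". SAP 2.1.1 makes Day 1 the first administration of study treatment. Placebo is study treatment: Protocol 6.7.2 says "All doses of study treatment (secukinumab and/or placebo) will be self-administered", and SAP 2.5.1 summarizes placebo doses under study treatment. A switcher's safety baseline therefore lies before the first placebo injection.

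**Columns.** SAP 2.3.1 counts switchers as placebo until the day before first secukinumab. After that: "Subsequently, they will be counted in Any AIN457 300mg Q2W or Any AIN457 300mg Q4W, respectively". Laboratory and other non-AE assessments "collected on the day of taking the first secukinumab dose will be counted in the placebo group". Adverse events are split by start date: "AEs that occur starting on the day of taking the first secukinumab dose will be counted in Any AIN457 300mg Q2W".

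**Tables.** SAP 2.6.3: "The number and percentage of subjects with CTCAE grade newly occurring or worsening after baseline will be presented". It also plans shift tables and maximum change from baseline. For the liver criteria: "The number and percentage of subjects with newly occurring liver enzyme abnormalities will also be summarized". SAP 2.6.4.1: "The number and percentage of subjects with newly occurring notable vital signs will be presented".

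No section of either document gives switchers a second baseline at Week 16.

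**The concern.** A column headed 'Any AIN457' is read as what happened on secukinumab. For patients randomized to secukinumab, the baseline is the value just before first secukinumab. For switchers it is a value taken 16 weeks earlier, and the Week 16 pre-dose value, which shows their state when secukinumab started, is not used. An abnormality that developed on placebo and simply carried on can therefore appear as new on drug.

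The SAP follows the start of secukinumab elsewhere. Adverse events are assigned by start date, and SAP Table 5-1 starts the 'Any AIN' exposure clock at the switch (an event on study day 110 counts as 10 days). The baseline-relative laboratory and vital-sign tables are the exception, and no reason is given.

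The 'Any AIN457' columns are the largest on-drug safety groups, and Protocol 4.5 names neutropenia as an observed risk. SAP 2.3.1 promises a placebo column only for exposure-adjusted tables, while SAP Table 2-3 gives laboratory and vital-sign notables crude incidence only. The affected tables therefore need not show the reader that a finding began on placebo.

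**Working it through.** The plan states no figure to reproduce here. The check applies the stated rule to possible grade paths, then estimates size from assumed rates.

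**1. Grade paths for a switcher.** Literal rule: worst post-switch grade exceeds the Day 1 grade. Alternative: worst post-switch grade exceeds the grade at the switch.

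| Day 1 → at switch → worst after switch | Literal rule | Baseline at first secukinumab |
|---|---|---|
| 0 → 1 → 1 (persists) | new | not new |
| 0 → 2 → 1 (improves, still above Day 1) | new | not new |
| 0 → 1 → 2 (worsens on drug) | new | new |
| 0 → 0 → 0 (grade 1 on placebo, resolved before switch) | not new | not new |
| 1 → 0 → 1 (cleared on placebo, returned on drug) | not new | new |

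The first two rows are the miscount. The fourth shows its limit: values up to and including the switch day stay in placebo. The last is an error of the opposite sign, if it is an error at all.

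**2. Denominators.** SAP 1.1 plans about 180 patients per secukinumab arm and about 180 over the two placebo arms, so about 90 switchers per regimen. Each regimen's 'Any' column has 180 + 90 = 270 patients, and switchers are 90/270 = one third.

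**3. Size with a constant hazard and no drug effect.** Let r be the risk by Week 52 (assumed) and π the proportion of placebo-onset abnormalities still present after the switch (assumed).

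- Onset on placebo: h = 1 − (1 − r)^(16/52).
- Onset on drug: (1 − h) × [1 − (1 − r)^(36/52)] = r − h.
- Switchers counted under the literal rule: πh + (r − h).
- 'Any' column: (2r + switcher rate)/3, so the excess is πh/3.
- Expected misattributed patients per regimen column: 90πh.

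At r = 5%: h = 1 − 0.95^(16/52) = 1.57% and onset on drug is 3.43%. With π = 1 the 'Any' column reads (10 + 5.00)/3 = 5.00%, against (10 + 3.43)/3 = 4.48% by drug onset.

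| r | h | 'Any', literal rule (π = 1 / 0.5) | 'Any' by drug onset | Excess, points (π = 1 / 0.5) | Patients per regimen (π = 1 / 0.5) |
|---|---|---|---|---|---|
| 0.5% | 0.15% | 0.50% / 0.47% | 0.45% | 0.05 / 0.03 | 0.14 / 0.07 |
| 2% | 0.62% | 2.00% / 1.90% | 1.79% | 0.21 / 0.10 | 0.56 / 0.28 |
| 5% | 1.57% | 5.00% / 4.74% | 4.48% | 0.52 / 0.26 | 1.41 / 0.70 |
| 10% | 3.19% | 10.0% / 9.47% | 8.94% | 1.06 / 0.53 | 2.87 / 1.44 |

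The patient counts assume no dropout before Week 16, so they are upper bounds for these inputs.

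**4. Size with fluctuating values.** Simulation with no drug effect, sampling at the scheduled laboratory visits (Day 1 and Weeks 2, 4, 8, 12, 16, 18, 20, 28, 44, 52), with 1 to 5% of samples low:

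- Between-patient variance share 0.5 to 0.7, no serial correlation: the two rules agree within 0.04 points in switchers because errors in both directions cancel. Still, about 9 to 20% of switchers counted as new were already low at Week 16.
- Residual correlation 0.7 to 0.85 per 4 weeks: the literal rule exceeds the Week 16 baseline by 0.24 to 1.62 points in switchers, which is 0.08 to 0.54 points in the 'Any' column (one third).
- Fully independent samples: net effect zero.

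**The case against.** **The text does not force the miscount.** SAP 2.6.3 does not say whether a grade first seen on placebo is tested again after the switch against Day 1, or credited once to the period in which it first appeared. Under the second reading the 0 → 1 → 1 path stays with placebo. The Programming Dataset Specifications, which might settle it, were not supplied. This stands as a limit on certainty. But the literal reading is the one given here, and SAP 2.5.1.1 cites those specifications for visit windows, not for baseline.

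**The size is easily overstated.** A reader might infer that every grade arising on placebo is charged to secukinumab. SAP 2.3.1 does not support that: only abnormalities still present after the switch can be counted. A reader might also infer that nearly a third of switcher events are misattributed (1.57/5.00 = 31% at r = 5%). That needs every placebo-onset grade to persist; at half persistence it is 0.785/4.22 = 19%. The documents give neither rate. And where one patient would matter most, for rare criteria, the expected error is well under one patient.

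**Cases can be traced.** All laboratory data are listed and abnormal values flagged, and the randomized Q2W and Q4W columns are unaffected. This stands, but listings do not correct a summary count.

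**A pre-study baseline is legitimate.** An abnormality present on Day 1 that cleared on placebo and returned on drug is arguably not new. This stands: that path is a matter of convention and is not relied on here.

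**Conclusion.** The point holds as a minor defect. Read literally, SAP 2.1.2 and 2.3.1 together count as newly occurring on secukinumab any laboratory grade, liver criterion or notable vital sign that arose on placebo and is still present, without worsening, at a post-switch visit. Shift and maximum-change tables share the misplaced baseline.

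The effect on an 'Any' column is about 0 to 0.5 points at assumed risks up to 5%, about 1 point at 10% with full persistence, and under one expected patient per regimen for rare criteria. These sizes rest on assumed risks, persistence and correlation, no drug effect, and planned numbers.

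A reader might go further and infer that the drug's safety comparison with placebo, or an efficacy result, is biased. The documents do not support that: the randomized columns use a baseline just before first secukinumab, and the affected tables are descriptive.

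**What to change.** Add to SAP 2.1.2: for the 'Any AIN457' columns of the newly-occurring, worsening, shift and maximum-change tables (laboratory CTCAE grades, liver criteria, vital signs), baseline is the last assessment on or before the day of first secukinumab. That is Day 1 for the randomized arms and normally the Week 16 pre-dose value for switchers. Keep the Day 1 baseline for the placebo period and for by-visit change from baseline.

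The cost is one sentence and one derived baseline variable. Hematology and chemistry are already scheduled at Week 16 (Protocol Table 16-1), and Protocol 8.4 has blood draws done before dosing. One side effect needs a footnote: an abnormality present on Day 1 that cleared on placebo and returned on secukinumab will now count as new.
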